IRT	interactive response technology
LS	least-squares
MADRS	Montgomery-Åsberg Depression Rating Scale
MAR	missing at random
MDD	major depressive disorder
MedDRA	Medical Dictionary for Regulatory Activities
MMRM	mixed model for repeated measures

Abbreviation	Definition
РК	Pharmacokinetic
РТ	preferred term
QD	once daily
RAS	randomized analysis set
REML	restricted maximum likelihood
SAP	statistical analyses plan
SAF	safety analysis set
SD	standard deviation
SDS	Sheehan Disability Scale
SE	standard error
SOC	system organ class
TBL	total bilirubin
TEAE	treatment-emergent adverse event
TRD	treatment-resistant depression
ULN	upper limit of normal
WHO	World Health Organization

1. INTRODUCTION

This document is the statistical analysis plan (SAP) for the Denovo Biopharma LLC (Denovo) study DB104-01 titled "A Biomarker-Guided, Randomized, Double-Blind, Placebo-Controlled Efficacy and Safety Study of Liafensine in Patients with Treatment-Resistant Depression." It is prepared based on Protocol Amendment 2 dated 29 Aug 2022 and Case Report Form (CRF) 1.0 dated 23 Mar 2023.

Populations for analysis, data handling rules, and statistical methods are described within this document. The statistical analyses and summary tabulations described in this document, including safety, tolerability, efficacy, and pharmacokinetics (PK), will provide the basis for the results sections of the clinical study report for this trial.

The statistical analysis for the study will be performed by NJS Associates, a Denovo-designated contract research organization.

1.1. Objectives

1.1.1. Primary Objective

The primary efficacy objective is to demonstrate that liafensine is superior to placebo in Denovo Genomic Marker 4 (DGM4)-positive patients with treatment-resistant depression (TRD) as assessed by the change in Montgomery-Åsberg Depression Rating Scale (MADRS) total score from baseline to Day 42 of double-blind treatment.

1.1.2. Secondary Objectives

The key secondary efficacy objective is to evaluate the change from baseline to Day 42 in DGM4-positive patients with TRD treated with liafensine vs placebo on the Clinical Global Impressions Scale-Severity (CGI-S).

Safety Objectives:

- To compare the safety and tolerability of liafensine vs placebo in all randomized patients with TRD who received at least one dose of study drug during double-blind treatment
- To evaluate safety for liafensine 1 mg once daily (QD) and 2 mg QD vs placebo in both DGM4-positive and DGM4-negative patients

Other Secondary Efficacy Objectives:

- To evaluate Clinical Global Impressions Scale-Improvement (CGI-I) at Day 42 in DGM4-positive patients with TRD treated with liafensine vs placebo
- To evaluate the change from baseline to Day 42 in DGM4-positive patients with TRD treated with liafensine vs placebo on the patient-reported functionality with Sheehan Disability Scale (SDS)

1.1.3. Exploratory Objectives

• To compare the proportion of DGM4-positive patients with TRD who respond to liafensine after 6 weeks of treatment vs placebo (response is defined as \geq 50% improvement from baseline in MADRS total score at Day 42)

- To compare the proportion of DGM4-positive patients with TRD who are in remission after 6 weeks of treatment with liafensine vs placebo (remission is defined as MADRS total score ≤ 10 at Day 42)
- To evaluate the change from baseline to Day 42 in DGM4-positive patients with TRD treated with liafensine vs placebo on MADRS anhedonia subscale and individual items
- To compare the efficacy of liafensine vs placebo in DGM4-negative patients with TRD, as assessed by change in MADRS total score from baseline to Day 42
- To evaluate efficacy for liafensine 1 mg QD and 2 mg QD vs placebo in both DGM4-positive and DGM4-negative patients
- To evaluate the PK of liafensine as part of the population PK analyses

1.2. Endpoints

1.2.1. Primary Endpoint

• Change in MADRS total score from baseline to Day 42, in DGM4-positive patients

1.2.2. Secondary Endpoints

Key Efficacy Endpoint:

• Change in CGI-S from baseline to Day 42, in DGM4-positive patients

Safety Endpoints:

- Adverse events (AEs) as characterized by type, frequency, severity, timing, seriousness, and relationship to study therapy
- Laboratory abnormalities as characterized by type, frequency, severity, and timing
- Vital signs including supine (after at least 5-min rest) and standing (after 1-min and 3-min standing), blood pressure (BP) and heart rate (HR), weight, electrocardiogram (ECG), clinical laboratory evaluation, Discontinuation-Emergent Signs and Symptoms (DESS) scale, and Columbia-Suicide Severity Rating Scale (C-SSRS) data

Other Secondary Efficacy Endpoints:

- CGI-I at Day 42, in DGM4-positive patients
- Change in SDS from baseline to Day 42, in DGM4-positive patients

1.2.3. Exploratory Endpoints

- Treatment response (defined as ≥ 50% improvement from baseline in MADRS total score at Day 42) in DGM4-positive patients
- Remission (defined as MADRS total score \leq 10 at Day 42) in DGM4-positive patients
- Change in MADRS anhedonia subscale and individual items from baseline to Day 42, in DGM4-positive patients
- Change in MADRS total score from baseline to Day 42, in DGM4-negative patients
- Change in MADRS total score from baseline to Day 42 in 1 mg QD group and 2 mg QD group, in both DGM4-positive and DGM4-negative patients

2. STUDY DESIGN

2.1. Design Overview

This study will be conducted as a multicenter, randomized, double-blind, placebo-controlled Phase 2b trial to assess the efficacy, safety, tolerability, and PK of liafensine. The study includes an up to 21-day screening period (the screening period may exceed 21 days if a prolonged washout is required).

Approximately 180 patients with TRD who meet all eligibility criteria will be randomized in a 1:1:1 ratio to receive either placebo QD, liafensine 1 mg QD, or liafensine 2 mg QD for 6 weeks. Approximately 150 randomized patients will be genotype GG for DGM4 (DGM4-positive) and approximately 30 randomized patients will be genotype AA or AG for DGM4 (DGM4-negative). DGM4 status (positive vs negative) of randomized patients will be blinded to the sites, patients, and sponsor. An interactive response technology (IRT) system will be used for blinding to DGM4 status, and to achieve the correct randomization ratio of DGM4-positive:DGM4-negative patients by randomly excluding most screened DGM4-negative patients (~80%). Randomization will be stratified by DGM4 status (positive vs negative) and region (North America vs Other). Patients who complete the study or discontinue after randomization will have 2 post-study follow-up visits (14 days after the last administered dose of study drug, and 28 days after the last administered dose of study drug); the 2nd follow-up visit will be conducted via phone call.

The overall study design is shown in Figure 1.

Figure 1. Study Design

Abbreviations: ATRQ = Antidepressant Treatment Response Questionnaire; DGM4 = Denovo Genomic Marker 4; HAMD-17 = Hamilton Depression Rating Scale - 17 Item; QD = once daily; R = randomization.

Patients will be randomly assigned through an IRT system in a 1:1:1 ratio to receive either placebo QD, liafensine 1 mg QD, or liafensine 2 mg QD for 6 weeks.

Randomization Phase:

Placebo QD

• Day 1 through Day 42: two placebo tablets QD

Liafensine 1 mg QD

• Day 1 through Day 42: one 1 mg liafensine tablet and one matching placebo tablet QD

Liafensine 2 mg QD

- Day 1 through Day 7: one 1 mg liafensine tablet and one matching placebo tablet QD
- Day 8 through Day 42: two 1 mg liafensine tablets QD

2.2. Schedule of Assessments

The schedule of assessments is found in Table 1 of the protocol. Study procedures and assessments are described in Section 7 of the protocol.

2.3. Sample Size Calculation

Eligible patients will be randomized 1:1:1 to receive placebo QD, liafensine 1 mg QD, or liafensine 2 mg QD. The primary analysis is to assess treatment difference in MADRS total score change from baseline (Visit 3, Day -1) to Visit 7 (Day 42), between the combined liafensine 1 mg QD and 2 mg QD doses vs placebo, in DGM4-positive patients. A sample size of 47 randomized DGM4-positive patients per arm is sufficient to detect a 4.5-unit difference between the combined liafensine 1 mg QD and 2 mg QD and 2 mg QD and 2 mg QD treatment groups and the placebo treatment group in the change in MADRS total score from baseline to Day 42 with 80% power at the 2-sided 0.05 alpha level, assuming a standard deviation (SD) of 9 units.

To compensate for potential loss of power due to randomized patients who do not take at least one dose of study drug or who do not have a post-randomization efficacy evaluation (~5%), a total of approximately 150 DGM4-positive patients (50 DGM4-positive patients per arm) will be randomized.

To examine trend in the total patient population and in the subgroup of DGM4-negative patients in order to evaluate DGM4 as a potential biomarker for predicting response to liafensine, approximately 20% additional DGM4-negative patients (10 per arm, total 30) will also be randomized. The sample size of 30 randomized patients in the DGM4-negative group is not estimated based on formal statistics in terms of power and alpha level.

Sample size re-estimation may be conducted if the percentage of missing data at Day 42 visit is higher than expected and/or if the observed variance is higher than the one assumed in the sample size estimation.

2.4. Timing of Analysis

2.4.1. Interim Analysis

No interim analysis will be performed.

2.4.2. Final Analysis

The final analysis for the clinical study report will be performed after the database has been locked and study has been unblinded.

3. GENERAL STATISTICAL CONSIDERATIONS

3.1. General Methods

Statistical analysis will be performed using SAS® software Version 9.4 or later (SAS 2001).

For continuous variables, descriptive statistics will include the number of subjects (n), mean, SD, median, minimum, and maximum. Frequencies and percentages will be displayed for categorical data. Percentages by categories will be based on the number of subjects including missing data, ie, will add up to 100%.

The estimated mean and median for a set of values should be calculated to one more decimal place than the raw (observed) data and rounded appropriately. Standard errors (SE) (or SD) should be calculated to two decimal places beyond the raw (observed) data and rounded appropriately. The decimal place for minimum and maximum should be the same as raw (observed) data. Percentage values should be reported with one digit to the right of the decimal point. When numerator value is "0," it should be displayed as "0." Further, a maximum of two decimal places will be used for all summary statistics unless otherwise specified.

Summaries presented by visit will be based on the scheduled assessments as planned in the protocol. Unscheduled assessments will not be included in the by-visit summary tables, however, will be included in the listings. Any unscheduled visit that falls within a visit window period without a scheduled visit will be used in summary tables. The summary tables and listings will be presented by DGM4 status (positive/negative) where noted, treatment group, and overall. The treatment groups are defined as:

- Placebo QD
- Liafensine 1 mg QD
- Liafensine 2 mg QD
- Liafensine 1 mg and 2 mg QD

3.2. Definition of Baseline

Baseline value is defined as the last available value collected before the first dose date of study drug for all safety laboratory, safety ECG, vital sign, and efficacy values.

3.3. Study Day

Study Day is relative to the start date of liafensine or placebo treatment:

- If analysis date is on or after the liafensine or placebo treatment start date, Study Day = analysis date - treatment start date + 1.
- If analysis date is before the liafensine or placebo treatment start date, Study Day = analysis date - treatment start date.

3.4. Study Visits

Study visits in the electronic data capture (EDC) datasets include Screening 1 (Visit 1) and Screening 2 (Visit 2), Day -1 (Visit 3), Day 7 (Visit 4), Day 14 (Visit 5), Day 28 (Visit 6), Day 42 (Visit 7/End of Treatment [EOT]), Day 14 and Day 28 post-last dose follow-up, and any unscheduled visits. Study visits will be windowed so that data recorded at any time have the potential to be included in summaries. The following visit window conventions will be followed:

Visit	Visit Number	Day	Window
Screening 1	1		
Screening 2	2		
Visit 3	3	-1	-1 to 3
Visit 4	4	7	4-10
Visit 5	5	14	11–20
Visit 6	6	28	21–34
Visit 7/EOT	7	42	35-49

Unscheduled visits will not be used in the summary by visit unless otherwise specified, the unscheduled visit values will be considered in the summary of worst change from baseline.

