- e Baseline evaluations will be performed on Day -1. Patients will be instructed to take the first dose of double-blind study drug the day after baseline evaluations (ie, on Day 1), and will be instructed to take double-blind study drug for the remainder of the 6-week treatment period.
- f For patients who discontinue early from the study, safety and efficacy determinations designated for Day 42 will be performed on the last day the patient takes a full dose of study drug or as soon as possible thereafter, but within 3 days of their last dose in any event.
- g At Visit 1, two brief ICFs will be obtained for the purpose of genotyping and biobanking, separately. A full ICF must be obtained at Visit 2.
- h Refer to Appendix 2 Preliminary Diagnosis Checklist
-  A separate blood sample (6 mL) will be collected for PGx (eg, determination of DGM4 status at Screening and for future research at Visit 5).
- The PRDF Checklist must be completed by the patient and reviewed by the rater 2 prior to CGI-S assessment. The baseline checklist entry must be compared by rater 2 against post-baseline entry to refresh the knowledge of patient's baseline condition prior to CGI-I assessment.
- k C-SSRS baseline/screening version
-  C-SSRS since-last-visit version
- m For randomized patients who complete the study or discontinue early, the DESS scale will be completed daily by the patient for 14 days post-last dose.
- n Vital signs should be taken prior to blood draws when applicable and include supine (after at least 5 min rest) and standing (after 1 min and 3 min standing), BP and heart rate, respiration rate, and temperature. Vital signs can be repeated for up to 3 occurrences after Visit 2 to see if values return to normal range, but any abnormality must be resolved by the Baseline Visit.
- o ECG recordings will be completed prior to blood draws when applicable and will be performed in triplicate (at 1-minute intervals between each of the three recordings) for baseline. Single ECG will be performed for rest of the timepoints.

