## 7.1.3. End-of-Treatment and Follow-up Evaluations and Procedures

Please see Table 1 for Day 42 EOT and Follow-up procedures and timing.

- Physical and neurological examinations
- Patient questionnaires and scales including MADRS, PRDF Checklist, CGI-S, CGI-I, SDS, C-SSRS (since-last-visit version), and DESS.
- Vital signs including supine (after at least 5 min rest) and standing (after 1 min and 3 min standing), blood pressure, heart rate, and body weight.
- ECGs will be performed on Day 42 (Visit 7) or at the time of early withdrawal, if within 3 days of last dose. Single 12-lead ECG will be performed.
- Clinical laboratory tests (including hematology, blood chemistry)
- Urinalysis (on-site unless macro-findings are observed and central lab assessment is required)
- Urine drug screen
- Serum pregnancy test
- Blood samples for PK per patient will be collected on Day 42 (Visit 7) or at the time of early withdrawal, if within 3 days of last dose. Time of last dose and time of blood collection will be recorded. When possible, and if medically appropriate, blood samples should be collected for PK from patients who experience an SAE or overdose.
- Assessment of adverse events
- Concomitant medications

Note: Rater 1 is to assess HAMD-17 and MADRS; rater 2 is to assess CGI-S after reviewing PRDF Checklist, and CGI-I after reviewing current and baseline PRDF Checklist and other baseline symptoms; the rest of scales maybe collected by either rater.

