5.5.4. DESS scale and C-SSRS data

Discontinuation-Emergent Signs and Symptoms scale and C-SSRS data will be summarized by descriptive statistics at each visit and by treatment group unless otherwise specified. Change from baseline at each visit will be presented using descriptive statistics by treatment group for C-SSRS. Please see Section 3.8.6 for details on DESS.

All DESS scale and C-SSRS data will be presented in a data listing.

5.5.5. 12-Lead Electrocardiograms

ECG parameters (Heart Rate, RR interval, QRS Duration, QT Interval, QTcF) will be assessed according to the schedule of assessments in Table 1 of the protocol.

12-lead ECG recordings will be performed in triplicate (at approximately 1-min intervals between each of the three recordings) at baseline, and single ECG for rest of visits.

QT corrected by Fridericia's formula is recommended: $QTcF = QT/RR^{0.33}$.

Actual value, change from baseline, and percent change from baseline at each visit (timepoint if applicable) will be presented using descriptive statistics by treatment group.

Shift of ECG overall interpretation from baseline to end of treatment visit will be prepared with number and percentage of subjects being reported with Normal, Abnormal, Abnormal Clinically Significant, and Not Done.

The QTcF interval will be summarized by the frequencies of subjects with absolute value and/or change from baseline using the criteria identified below:

- <450
- \geq 450 to < 480
- ≥ 480 to < 500
- ≥ 500
- <30 increases from baseline
- 30 to ≤ 60 increases from baseline
- > 60 increases from baseline

Subjects with abnormal ECG results, regardless of clinical significance, will be identified in data listings with flags for abnormalities.

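### SAP 3.4 windows an early-termination ECG taken before Day 35 away from Visit 7/EOT, so it leaves the EOT row and the baseline-to-EOT ECG shift table

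*SAP*

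**What the plan says.** Protocol Table 1 marks the 12-lead ECG at Visits 2, 3 and 7 only, so one ECG is scheduled after baseline. Protocol 7.1.3 puts it this way: "ECGs will be performed on Day 42 (Visit 7) or at the time of early withdrawal, if within 3 days of last dose". For patients who leave early, Table 1 footnote f says that "safety and efficacy determinations designated for Day 42 will be performed on the last day the patient takes a full dose of study drug". Where that is not feasible, the footnote allows a short delay, "but within 3 days of their last dose in any event".

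SAP 3.4 names the visits held in the EDC system, including Visit 7/EOT, and then says: "Study visits will be windowed so that data recorded at any time have the potential to be included in summaries". It continues, "The following visit window conventions will be followed", and gives these study-day windows: Visit 3, -1 to 3; Visit 4, 4-10; Visit 5, 11-20; Visit 6, 21-34; Visit 7/EOT, 35-49. SAP 3.3 counts from the first dose: "Study Day = analysis date - treatment start date + 1". No line covers an end-of-treatment record collected early.

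SAP 5.5.5 asks for three ECG summaries: values and changes at each visit; a shift table ("Shift of ECG overall interpretation from baseline to end of treatment visit will be prepared"); and counts of QTcF categories, for which no visit is named. Abnormal ECGs are also flagged in listings. On by-visit tables in general, SAP 3.1 says: "Summaries presented by visit will be based on the scheduled assessments as planned in the protocol".

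**The concern.** The day windows suit MADRS and CGI-S, which are measured at every on-treatment visit: an early-termination score moves to the scheduled visit nearest in time, where other patients have scores too. The ECG has no such place to go. Between baseline and Visit 7 no ECG is scheduled, so a re-filed ECG stands almost alone at Visit 4, 5 or 6 and is missing where the comparison is made.

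The protocol takes this ECG deliberately, so that patients who stop early still have an end-of-treatment reading. Under the windows, the EOT shift table would leave these patients out or count them as not done although a reading exists. Such an omission is selective. Adverse events are one of the listed reasons for stopping (SAP 5.1.1 and 5.4.1.1), ECG data are a listed safety endpoint (SAP 1.2.2), and the safety set is everyone dosed (SAP 4.3). The laboratory shift table in SAP 5.5.2 is not exposed in this way, because it uses the maximum post-baseline value and so does not depend on a visit label.

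**Working it through.** **Inputs.** Windows from SAP 3.4; first dose = Day 1 from SAP 3.3; lag from last dose to ECG of 0 to 3 days from Protocol Table 1 footnote f; about 180 patients randomized 1:1:1 from SAP 2.1, so 180 / 3 = 60 per arm.

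**Step 1: reproduce the windows.** The midpoints between the nominal days are (-1 + 7)/2 = 3, (7 + 14)/2 = 10.5, (14 + 28)/2 = 21 and (28 + 42)/2 = 35. These give -1 to 3, 4-10, 11-20, 21-34 and 35 onward, with an upper limit of 42 + 7 = 49. This matches the SAP table, so the windows are built on study day alone and take no account of which assessments a visit includes.

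**Step 2: map each last-dose day from 1 to 34.** ECG day = last-dose day + lag. Number of last-dose days falling in each window:

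| Lag (days) | Visit 3 | Visit 4 | Visit 5 | Visit 6 | Visit 7/EOT |
|---|---|---|---|---|---|
| 0 | 3 | 7 | 10 | 14 | 0 |
| 1 | 2 | 7 | 10 | 14 | 1 |
| 2 | 1 | 7 | 10 | 14 | 2 |
| 3 | 0 | 7 | 10 | 14 | 3 |

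At every lag, 7 + 10 + 14 = 31 of the 34 days land at a visit with no scheduled ECG. An ECG on Days 1-3 falls in the Visit 3 window. It does not replace the baseline value, because SAP 3.2 takes the last value before the first dose, but it still misses EOT. The ECG reaches the EOT window only when the last dose is on Day 32, 33 or 34 and the lag carries it to Day 35 or later. These are counts of calendar days, not of patients.

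**Step 3: which outputs change.**
- EOT row of the by-visit summary: loses the record.
- Baseline-to-EOT shift: loses the record.
- QTcF categories: no visit is named, so the record is not excluded.
- Listings: unaffected.

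**Step 4: possible size.** The documents give no early-stopping rate. The 5% in SAP 2.3 covers only patients with no dose or no post-randomization efficacy evaluation. Assume that 10-20% leave before Day 35, each with an ECG that falls outside the EOT window:
- per arm: 0.10 × 60 = 6 to 0.20 × 60 = 12, leaving 54 to 48 in the EOT row if everyone else has an ECG;
- whole trial: 0.10 × 180 = 18 to 0.20 × 180 = 36.

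**Step 5: with the fix.** All 34 last-dose days reach the EOT outputs, at any lag up to 3 days.

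**The case against.** The best reply is that the nominal visit label could govern. SAP 3.4 lists Visit 7/EOT as an EDC visit, the protocol treats the early-withdrawal ECG as the Visit 7 ECG, SAP 5.5.5 refers to an end-of-treatment visit and not to a range of days, and SAP 3.1 ties by-visit tables to the planned assessments. On that reading nothing is lost. This stands as a possible reading, but SAP 3.4 states a windowing rule without exception and the SAP does not say which rule takes precedence. Two programmers could produce different EOT tables from the same data.

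The reply is also right to limit the scope. A reader might infer any of the following, and the documents do not support them:

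- *Everyone who stops before Day 35 is affected.* Last doses on Days 32-34 can still give an ECG inside the window, and Protocol 4.4.1 encourages patients who stop treatment to remain in the study, so some may have an ECG at Day 42.
- *The ECG disappears from the analysis.* Windowing moves it to another visit row; the QTcF counts and listings can still contain it.
- *Detection of QTcF outliers is weakened.* A zero-event upper bound of 3/n would go from 3/60 = 5.0% to 3/54 = 5.6% or 3/48 = 6.3%, but that bound belongs to the QTcF category analysis, whose denominator the windows do not reduce.
- *The ECG comparison is biased toward no effect.* The documents show neither an imbalance in early stopping nor an ECG signal, so the direction is unknown.

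**Conclusion.** The point holds for two descriptive outputs: the Visit 7/EOT row of the by-visit ECG summary and the baseline-to-EOT shift of overall ECG interpretation. Under SAP 3.4 as written, both would mainly describe patients still assessed at Day 35 or later and would selectively omit early stoppers, including those who stop for adverse events. That population does not match the safety set.

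The conclusion assumes that the study-day window overrides the EDC label, which is the plain reading of SAP 3.4. The number affected cannot be derived from the documents; about 6-12 of 60 per arm is an illustration that rests on the assumed 10-20%. The primary analysis is not touched. This is a cheap improvement, not a threat to the trial's conclusions.

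**What to change.** Add to SAP 3.4, with a cross-reference in 5.5.5: for the EOT row and the EOT shift of the 12-lead ECG, the EOT record is the one collected as Visit 7/EOT or early termination, whatever its study day, if it was taken within 3 days of the last dose. The 3-day limit is the protocol's own. It also settles which record counts when a patient who stopped treatment has a later ECG off drug.

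Footnote both tables to say that treatment durations are mixed. Keep the day windows for MADRS and CGI. State that the QTcF categories use all post-baseline ECGs; tying them to the EOT record alone could exclude an unscheduled on-treatment ECG with a high value.

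The cost is a short SAP addition and a visit-mapping exception in the ECG dataset. No new data are needed. The one drawback is the mixture of durations in the EOT row, which the footnote discloses.
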